3.10 Randomization

The randomization of the patients will be performed using a dedicated software with a 1:1 allocation ratio. The allocation group will be concealed with opaque envelopes.

3.11 Blindness

There will be no blindness at the level of the patient, the treating physicians (surgeon, oncologist, radiotherapist) and the researcher who will record the data.

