3.4 Study Arms

In this study there will be two arms [5, 10]. Patients that are randomized in the first arm will receive neoadjuvant chemoradiotherapy and consolidation chemotherapy and then undergo surgical resection of the tumor. In the second arm, patients will receive the standard long-course neoadjuvant chemoradiotherapy regimen and then undergo tumor resection. The treatment will be completed with adjuvant chemotherapy. In both groups, surgery will follow the principles of total mesorectal excision (TME).

The control group will receive the standard 5-week neoadjuvant chemoradiotherapy regimen. Six weeks after completion the patient will be re-staged with rectal MRI and depending on the response will be operated (TME): immediately in case of non-response (mrTRG 5) or after an additional 6-week delay (overall 12 weeks after the end of chemoradiotherapy) in case of partial response (mrTRG 2-4). Adjuvant chemotherapy will be, also, administered.

The experimental group will receive the standard 5-week neoadjuvant chemoradiotherapy (CRT). Thereafter, all patients will commence consolidation chemotherapy. At the 6th week after the end of CRT, patients will undergo MRI re-staging: In case of non-response (mrTRG 5) they will be submitted immediately to surgery, and, subsequently, excluded from the trial. In case of response (mrTRG 2-4) they will receive consolidation chemotherapy for the whole waiting period between the end of CRT and surgery - 12 weeks.

The following interventions will be introduced:

Neoadjuvant Chemoradiotherapy. 5-week neoadjuvant radiotherapy regimen (28 x 1.8 Gy) combined with Capecitabine (bid 800 mg/m², twice daily, on days 1-33-38)

Consolidation Chemotherapy. CAPOX (Capecitabine bid 1000 mg/m² and Oxaliplatin 130 mg/m², day 1, every 3 weeks) or alternatively FOLFOX

Adjuvant Chemotherapy. 8 cycles of CAPOX (Capecitabine bid 1000 mg/m², twice daily, day 1-14, every 3 weeks and Oxaliplatin 130 mg/m², day 1, every 3 weeks) or alternatively, 12 cycles of folinate, fluorouracil and oxaliplatin (FOLFOX)

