3.7 Primary endpoint

Disease Free Survival. Occurrence of Disease Free Survival. If such an episode occurs, then it will be defined as=1 'YES' If such an episode does not occur, then it will be defined as=0 'NO'. [Time Frame: 3 years postoperatively]

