3.13 Monitoring

Following hospital discharge, the patient will be called for reassessment at one month after the operation. Patients will be included in the standard monitoring protocol (CT, MRI, cancer markers), unless otherwise required. At the same time, the pathological assessment of the specimen will be recorded. In addition, at 3 and 5 years postoperatively, overall, disease-free survival and recurrence rates will be recorded.

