3.15 Study Group

All participating members have years of experience in their field and have, therefore, completed the learning curve for the required techniques. Data collection and recording will be carried out by an independent, third party, researcher.

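### The independent data recorder is declared unblinded, and no masked reading of MRI, CT or pathology is provided for, although recurrence, mrTRG, pathological response and margins rest on those reads

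*Protocol*

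**What the plan says.** Protocol section 3.11 lists who is not blinded: the patient, the surgeon, the oncologist, the radiotherapist and "the researcher who will record the data". Section 3.15 describes the person in that last role: "Data collection and recording will be carried out by an independent, third party, researcher". The radiologist and the pathologist do not appear in the list, and no section says whether they know the arm.

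The outcomes that depend on reading an image or a specimen are these:

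- **Primary endpoint (3.7).** "Disease Free Survival. Occurrence of Disease Free Survival", coded yes or no, with "Time Frame: 3 years postoperatively". Section 3.7 gives no definition of an event and names no assessor.
- **Recurrence (3.8 and 3.13).** It is detected through routine follow-up: "Patients will be included in the standard monitoring protocol (CT, MRI, cancer markers), unless otherwise required".
- **Pathological response and margins (3.8 and 3.13).** Section 3.13 says that "the pathological assessment of the specimen will be recorded" and does not say under what conditions it is made.
- **mrTRG at week 6 (3.4).** It determines the timing of surgery in both arms. In the experimental arm it also determines who stays in the trial: "In case of non-response (mrTRG 5) they will be submitted immediately to surgery, and, subsequently, excluded from the trial".

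**The concern.** The treatments differ too visibly for patients or clinicians to be masked, so open-label treatment is unavoidable. Open-label assessment is not. The protocol sets up a recorder who is independent, then declares that person unblinded without giving a reason, and it builds in no masked step before the data reach that person.

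Recurrence on a follow-up scan and a borderline mrTRG 4 or 5 can be matters of judgement. A reader who knows the arm may resolve a doubtful case differently in the two arms, even without intent. For recurrence this acts directly on the primary endpoint. For mrTRG it acts on which experimental-arm patients remain in the trial. The planned number of events is small, so there is little to dilute a shift of one or two calls.

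**Working it through.** **Inputs.** From section 3.9: hazard ratio 0.23, alpha 5%, power 90%, dropout 15%, 42 patients per group. Alpha is taken as two-sided, because the protocol does not say. The protocol states neither a number of events nor a control-arm disease-free survival (DFS) rate.

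**1. The stated sample size.** The figure of 42 cannot be checked from the stated inputs alone, but it is reachable. Assume control 3-year DFS of 55%. Experimental DFS is then 0.55^0.23 = 0.872, and the event probabilities are 0.450 and 0.128. Twenty events need 20 / 0.578 = 34.6, so 35 per arm, and 35 / 0.85 = 41.2, so 42.

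**2. Events implied by the design.**

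- Schoenfeld: 4 × (1.960 + 1.282)² / (ln 0.23)² = 4 × 10.507 / 2.160 = 19.5, so 20.
- Freedman: 10.507 × (1.23 / 0.77)² = 26.8, so 27.

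About 20 is therefore a fair figure; the more conservative formula gives 27.

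**3. Split expected at the planned effect.** Evaluable patients per arm are 42 × 0.85 = 35.7, so 36. With 20 events in total and a hazard ratio of 0.23, about 15.6 fall in the control arm and 4.4 in the experimental arm, roughly 16 v 4.

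**4. Effect of changing one call.** Fisher exact test, two-sided, 36 per arm, control v experimental:

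| Starting table | p | After the change | p |
|---|---|---|---|
| 16 v 4 (about as planned) | 0.003 | 15 v 4 | 0.007 |
| 16 v 4 | 0.003 | 16 v 5 | 0.009 |
| 16 v 4 | 0.003 | 15 v 5 (one in each arm) | 0.017 |
| 14 v 5 (near threshold) | 0.031 | 13 v 5 | 0.055 |
| 14 v 5 | 0.031 | 13 v 6 (one in each arm) | 0.107 |
| 14 v 6 (just short) | 0.064 | 14 v 5 | 0.031 |

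One call leaves a result of the planned size significant. Near the threshold, one call can remove significance or create it.

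**5. How often a result lies that close.** Suppose the hazard ratio really is 0.23, with 36 per arm and Fisher's test. The share of significant results that one changed call would undo is about 12% if control 3-year DFS is 55%, about 20% if it is 65% and about 35% if it is 75%. These DFS rates are assumptions. If the true hazard ratio were 0.5, the share over the same range would be 30% to 48%.

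These are fixed two-by-two tables. A log-rank analysis would give somewhat different values.

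**The case against.** Five points can fairly be made on the other side.

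- **Independence and lack of masking are compatible.** Sections 3.11 and 3.15 do not contradict each other, and an openly declared open-label trial is a legitimate design. This stands: the point concerns an avoidable risk of bias, not an inconsistency.
- **The recorder cannot be fully masked.** Section 3.8 includes treatment compliance and chemotherapy toxicity. Compliance cannot be scored without knowing whether chemotherapy was due before or after surgery. This also stands, so the remedy should act on the readers and not on the recorder.
- **Silence is not a statement.** A reader might infer that the radiologist and pathologist are unmasked. The protocol does not say so, and they are not on its unblinded list. What can be said is that no masked reading is provided for.
- **The numerical example is chosen.** The table 14 v 5 corresponds to a hazard ratio of about ln(31/36) / ln(22/36) = 0.30, not 0.23. A reader might infer that one subjective call would decide the primary result; at about the planned split it would not. Sensitivity to one event also reflects the small number of events and does not itself show harm from unblinding. The documents give no rate of equivocal reads, so the size of any shift is unknown. Any deaths counted in DFS are not subjective.
- **The one-arm exclusion is a different matter.** Perfectly masked MRI would still leave mrTRG 5 patients excluded from one arm only. Masking would protect the reading, not the rule, and this point should not draw its weight from that rule.

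The documents also say nothing about cost, so a claim that masking would be free has no support in them.

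**Conclusion.** The concern holds in a limited form. The protocol leaves an independent recorder unblinded and provides no masked reading for the imaging and pathology behind recurrence, mrTRG, response and margins, although clinicians outside the declared unblinded list could plausibly supply it.

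The consequence is a risk of bias that matters most for a result near the significance threshold, where a single call can move p from 0.031 to 0.055, or from 0.064 to 0.031. It would not overturn a result of the planned size (16 v 4, p = 0.003). The size rests on two-sided 5%, about 20 events by Schoenfeld, 36 evaluable patients per arm and Fisher's test, which is a choice made here because the protocol names no primary test. No direction or amount of actual bias can be derived from the documents. This is worth correcting, but it is not fatal to the trial.

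**What to change.** Amend section 3.11 in three respects:

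1. State that the radiologist reading re-staging and follow-up scans, and the pathologist reading the specimen, report from request forms that omit the arm.
2. State that the recorder transcribes mrTRG, recurrence status and date, pathological response and margin status from those reports without reinterpreting them.
3. Allow the recorder to remain unblinded for compliance and toxicity.

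The cost is protocol wording, a modified request form and slightly more paperwork. It uses readers whom the trial already needs and changes neither treatment nor sample size. The downside is that masking will sometimes be broken, for example by visible treatment timing or by the hospital record. The one-arm exclusion of mrTRG 5 patients in section 3.4 needs to be dealt with separately.

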3.12 Exit criteria

The patient will be discharged when it is ensured that is medically safe to be released. The exit time will be regarded as the time that the patient will fulfill the Clinical Discharge Criteria. More specifically, the patient should display the following: steady vital signs, fully oriented, without nausea or vomiting, mobilized with a steady gait and without a notable bleeding [22].

3.13 Monitoring

Following hospital discharge, the patient will be called for reassessment at one month after the operation. Patients will be included in the standard monitoring protocol (CT, MRI, cancer markers), unless otherwise required. At the same time, the pathological assessment of the specimen will be recorded. In addition, at 3 and 5 years postoperatively, overall, disease-free survival and recurrence rates will be recorded.

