1. INTRODUCTION

1.1 Literature Review

Colorectal cancer is the second leading cause of cancer-related deaths worldwide. It is estimated that 10% of cancer mortality is attributed to malignant neoplasms of the colon and rectum [1]. More specifically, in the United States alone, 53,200 colorectal cancer deaths were reported [2].

The current treatment of choice for locally advanced rectal cancer (Stage II/ III) is the combination of neoadjuvant chemoradiation followed by radical surgical resection based on the principles of total mesorectal excision (TME) after a 8-12 weeks period [3]. Therapy is usually completed with the administration of adjuvant chemotherapy based on oxaliplatin and fluoropyrimidines. This combined approach allowed the reduction of local recurrence at levels around 5%. Despite the impressive results in local control, the same was not confirmed for the long-term, overall survival. Possible explanations to that are: a) the compliance and completion of the treatment schemes during the postoperative period were low and b) there was a delay in the administration of adjuvant chemotherapy; both could lead to subclinical metastatic disease progression [4].

On the basis of achieving both goals, (i.e., local control through neoadjuvant radiotherapy and metastatic disease control through systemic chemotherapy) the administration of the two therapies in the preoperative period was proposed, in the form of combined or total neoadjuvant therapy [1, 5–8].

Additional theoretical benefits of total neoadjuvant therapy are faster defunctioning stoma reversal, as well as the possibility of a more accurate evaluation of the tumor biological behavior, thus enabling a safer staging for patients who would be candidates for a watch and wait protocol [1–3, 5–12]. Furthermore, for patients who will eventually undergo surgery, total neoadjuvant therapy could probably increase R0 resection and sphincter-preservation rates [3, 5, 8– 10, 12].

However, many researchers question the safety and efficacy of total neoadjuvant therapy [7, 13]. First, the administration of neoadjuvant chemotherapy significantly increases the risk of

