severe toxicity from cytotoxic agents [14]. At the same time, according to the results of one of the largest prospective randomized trials, the addition of neoadjuvant chemotherapy into the treatment algorithm did not offer any advantage in the pathological response, 5-year overall and disease-free survival rates [15]. Finally, there is considerable heterogeneity in the current literature, most likely reflecting the different schemes used in different trials regarding the radiotherapy regimen, the chemotherapy regimen as well as the sequence of each one in each protocol [16].

We believe it is difficult to interpret any differences in results when multiple parameters have been changed in a comparative trial [17]. For this reason, when testing our current standard neoadjuvant protocol to the new trend of total neoadjuvant therapy we decided to keep the same scheme and timing for the experimental group also, and the only parameter which is different is the use of the classic chemotherapy scheme during the waiting period following chemoradiation and before surgery [18].

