3.8 Secondary endpoints

Secondary endpoints of the present study are:

Complete Pathological Response. Occurrence of Complete Pathological Response. If such an episode occurs, then it will be defined as=1 'YES' If such an episode does not occur, then it will be defined as=0 'NO'. [Time Frame: 1 month postoperatively]

Postoperative Complications. Occurrence of postoperative complications based on the Clavien Dindo Classification [20]. If such an episode occurs, then it will be defined as=1 'YES' If such an episode does not occur, then it will be defined as=0 'NO'. [Time Frame: 1 month postoperatively]

Length of Hospital Stay. Postoperative time that the patient can be safely discharged. Measurement unit: days. The patient will be discharged, when it is ensured that is medically safe

to be released. In particular, as the exit time of the patient, will be regarded the time that the patient will fulfil the Clinical Discharge Criteria. [Time Frame: Maximum time frame 39 days postoperatively]

Readmission. Occurrence of postoperative readmission. If such an episode occurs, then it will be defined as=1 'YES' If such an episode does not occur, then it will be defined as=0 'NO'. [Time Frame: 1 month postoperatively]

Negative Resection Margin. Occurrence of Negative Resection Margin. If such an episode occurs, then it will be defined as=1 'YES' If such an episode does not occur, then it will be defined as=0 'NO'. [Time Frame: 1 month postoperatively]

Overall Survival. Occurrence of Overall Survival. If such an episode occurs, then it will be defined as=1 'YES' If such an episode does not occur, then it will be defined as=0 'NO'. [Time Frame: 3 years postoperatively]

Chemotherapy Toxicity. Occurrence of Chemotherapy Toxicity. If such an episode occurs, then it will be defined as=1 'YES' If such an episode does not occur, then it will be defined as=0 'NO'. [Time Frame: 3 years postoperatively]

Local Recurrence. Occurrence of Local Recurrence. If such an episode occurs, then it will be defined as=1 'YES' If such an episode does not occur, then it will be defined as=0 'NO'. [Time Frame: 3 years postoperatively]

Treatment Compliance. Occurrence of Treatment Compliance. If such an episode occurs, then it will be defined as=1 'YES' If such an episode does not occur, then it will be defined as=0 'NO'. [Time Frame: 3 years postoperatively]

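### Overall survival, disease-free survival and recurrence are recorded at 5 years, but their endpoints stop at 3 years, so the 5-year data have no defined role and the survival comparison omits deaths already collected

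*Protocol*

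**What the plan says.** Protocol section 3.13 (Monitoring) sets two recording times for three outcomes: "at 3 and 5 years postoperatively, overall, disease-free survival and recurrence rates will be recorded".

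The endpoint sections use only the first of these times. In section 3.7 the primary endpoint, DFS, is coded 1/0 with "Time Frame: 3 years postoperatively". In section 3.8, OS ("Overall Survival. Occurrence of Overall Survival. If such an episode occurs, then it will be defined as=1 'YES") and local recurrence ("Local Recurrence. Occurrence of Local Recurrence. If such an episode occurs, then it will be defined as=1 'YES") are coded the same way, also at 3 years. No primary or secondary endpoint has a 5-year time frame, and the objective in section 2.1 does not mention one.

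As background, section 1.1 says of the gain in local control that "the same was not confirmed for the long-term, overall survival". It also cites an earlier randomised trial that found no advantage in, among other outcomes, "5-year overall and disease-free survival rates".

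**The concern.** Three outcomes have two planned recording times, and only one of those times is tied to an endpoint. This has two consequences.

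First, nothing in the protocol says whether the 5-year results are a prespecified comparison or descriptive follow-up. The trial is open-label, including for the researcher who records the data (section 3.11), so that status is better settled before the results are seen.

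Second, OS in a trial of 84 patients rests on few deaths. A yes/no outcome at 3 years discards the later deaths, although the trial already plans to record them. Precision is lost that would cost no extra patients and no extra follow-up.

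**Working it through.** **Inputs from the protocol.** 84 patients, 1:1, 15% dropout, DFS hazard ratio (HR) 0.23, alpha 5%, power 90% (sections 3.9 and 3.10); recording at 3 and 5 years (3.13). The protocol gives no OS rate, control DFS rate or expected number of events. The rates below are assumptions and are shown as ranges.

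**The plan's own figure.** The only stated figure is 42 per group. With HR 0.23, two-sided 5% and 90% power, Schoenfeld's formula gives 4(1.960 + 1.282)² / (ln 0.23)² = 19.5, so 20 events. Evaluable patients are 84 × 0.85 = 71.4. Twenty events among them corresponds to a control 3-year DFS of about 56%. The figure of 42 is therefore reachable, but it cannot be verified from the stated inputs. The OS calculation needs only the 71.4.

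**Deaths at 3 and 5 years.** Under a constant hazard, if S is 3-year OS, then 5-year OS is S^(5/3). The ratio of deaths is (1 − S^(5/3)) / (1 − S), the shortfall at 3 years is 1 − 1/ratio, and the standard error of the log HR falls by 1 − 1/√ratio.

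| Assumed 3-year OS | Ratio of deaths, 5 y to 3 y | Fewer deaths at 3 y | Fall in SE |
|---|---|---|---|
| 95% | 1.64 | 39% | 22% |
| 90% | 1.61 | 38% | 21% |
| 85% | 1.58 | 37% | 20% |
| 80% | 1.55 | 36% | 20% |

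**In patients.** At 3-year OS of 90%, deaths are 71.4 × 0.100 = 7.1 at 3 years and 71.4 × 0.161 = 11.5 at 5 years. At 85% they are 71.4 × 0.150 = 10.7 and 71.4 × 0.237 = 16.9. The approximate 95% confidence interval multiplies and divides the HR by exp(1.96 × 2/√deaths). That factor falls from 4.3 to 3.2 at 90%, and from 3.3 to 2.6 at 85%.

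**Sensitivity to the hazard shape.** With Weibull hazards and 5-year OS of 65–85%, the shortfall is about 26–28% if the hazard falls over time (shape 0.7) and about 48–52% if it rises (shape 1.5).

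**Power for OS.** With 84 patients, control 5-year OS of 75% and a true HR between 0.7 and 0.5, two-sided power is about 9–20% at 3 years and 12–29% at 5 years.

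**Would a 5-year confirmatory DFS analysis help?** Simulated log-rank power, 36 per arm, 4,000 runs, HR 0.23 up to year 3 (simulation error about 1.5 points):

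| Control 3-year DFS | 3-year analysis | 5-year, HR stays 0.23 | 5-year, HR 0.6 after year 3 | 5-year, no effect after year 3 |
|---|---|---|---|---|
| 57% | 87% | 96% | 84% | 61% |
| 65% | 77% | 92% | 74% | 49% |
| 70% | 70% | 88% | 66% | 42% |
| 75% | 62% | 81% | 58% | 36% |

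The gain appears only if the very large effect persists unchanged through year 5.

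**The case against.** The strongest reply is that nothing here contradicts itself. The 3-year recording matches the 3-year endpoints, following patients beyond the endpoint horizon is ordinary practice, and a statistical analysis plan that is not shown may describe a 5-year analysis. The recording is also stated in advance, so a 5-year report would not be post hoc data collection. Most of this stands: the extra recording is not an error. But endpoints and time frames are fixed in sections 3.7 and 3.8 of this protocol, and as written the OS endpoint ignores deaths that section 3.13 collects.

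The practical effect is also modest. OS is one of nine secondary endpoints and remains underpowered at 5 years. That stands fully.

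A reader might infer more than the protocol supports in four ways:

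- *That every efficacy endpoint stops at 3 years.* Complete pathological response and negative resection margin are assessed at 1 month. The mismatch concerns DFS, OS and local recurrence.
- *That 40% of deaths are lost.* The protocol contains no mortality figure. Under a constant hazard, 40% is (5 − 3)/5, a limit approached only as mortality tends to zero.
- *That the rationale commits the trial to 5-year survival.* Section 1.1 speaks of long-term survival without naming a year, and its 5-year figures describe another trial's result. Neither is an objective of this trial.
- *That the confirmatory DFS analysis should move to 5 years or wait for a set number of events.* The power gain needs HR 0.23 to last to year 5. If the effect wanes, 5-year power is no better than 3-year power and can be much worse.

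**Conclusion.** The point holds in a limited form. OS, DFS and recurrence will be recorded at 5 years without a defined role, and the OS comparison as written forgoes about 36–39% of the deaths available by 5 years. That range assumes a constant hazard and 3-year OS of 80–95%; a falling or rising hazard widens it to roughly 26–52%. Using all follow-up lowers the standard error of the log HR by about 20–22% under the constant-hazard assumption. This is a worthwhile gain in precision from data already planned. It does not make OS confirmatory, and it gives no reason to change the timing of the primary DFS analysis.

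**What to change.** In section 3.8, define Overall Survival as time from a stated origin to death from any cause, using all follow-up to 5 years, with the 3-year value also reported. Name 5-year DFS and 5-year recurrence as secondary endpoints. Keep the primary DFS analysis in section 3.7 at 3 years. In section 3.13, say that dates of death and of last contact are recorded, because a time-to-event analysis needs them and the section mentions only rates.

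The cost is wording and a little more analysis. No patients or follow-up visits are added. The one trade-off is that the full OS result is available only at 5 years, while the 3-year value can still be reported on the present schedule.
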